The primary objective of Arm B is to determine the MTD, defined by acceptable toxicity, of pembrolizumab combined with decitabine and pralatrexate from among the six study dose combinations in the following table, and to evaluate efficacy, as determined by overall response rate, at the estimated MTD. In a previous version of the protocol (dated 14 Dec 2022), fifteen dose combinations were considered for Part B. While the current protocol version reduces the number of dose combinations to six, we have maintained the original combination labels to maintain consistency with the original dose levels for each combination.

Combination designation			
Pralatrexate	20mg/m  1,8,15	Combination 6	Combination 8
	20mg/m  1,15	Combination 3	Combination 5
	15mg/m  1,15	Combination 1	Combination 2
		10mg/m  1-3	10mg/m  1-5
		Decitabine	

Based on the accumulated data from the first 4 subjects (1 observed DLT) accrued to Combination 8 in Arm B, the next eligible subject in Arm B will be entered onto Combination 8.

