## 10.2 Dose allocation

### Arms A and C

Dose allocation in Arms A and C will be based upon a continual reassessment method (CRM), which uses a model for the probability of DLT and the accumulated DLT data at each dose level to sequentially allocate each new patient cohort. Toxicity assessment is based on the occurrence of DLTs, and the minimum follow-up for determination of escalation is one cycle of treatment. The DLT probabilities are modeled using a one-parameter working model  $R(d_i) = \Pr(\text{DLT at dose level } i) \approx \alpha_i^{\exp(a)}$ , where  $\alpha_i$  is the skeleton of the working model. The skeleton values are pre-specified constants and were chosen according to the algorithm of Lee and Cheung, which yields a working model that results in well-performing operating characteristics in a broad range of scenarios. For this study, the skeleton values are  $\alpha_i = (0.08, 0.15, 0.25)$ . Based on the available DLT data  $D = \{(y_i, n_i); i = 1, \dots, 3\}$ , where where  $y_i$  is the number of DLT's and  $n_i$  is the number of subjects treated on study dose level  $i$ , the likelihood is given by  $L(a) \propto \prod_{i=1}^3 (\alpha_i^{\exp(a)})^{y_i} (1 - \alpha_i^{\exp(a)})^{n_i - y_i}$ .

After accrual of each patient into the trial, the DLT probability estimates,  $\tilde{R}(d_i)$ , are updated via  $\tilde{R}(d_i) = \alpha_i^{\exp(\tilde{a})}; \quad \tilde{a} = \arg \max L(a)$ .

These estimates are used to sequentially allocate patients to the dose indicated by the modeling to have the estimated DLT rate closest to 25%. The study will accrue participants in cohorts of size 1 and dose levels will not be skipped. The coherence principle will be used, where the next patient will not be treated at a dose level higher than the current dose level if the current patient experiences a DLT. Additionally, the next patient will not be treated at a dose level lower than the current dose level if the current patient does not experience a DLT. The study will sequentially repeat the estimation procedure after the enrollment and follow-up of each cohort. The allocation procedure will be repeated until sufficient information about the MTD has been obtained according to the stopping rules described below.

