$$L_m(\theta_m) = \prod_{i \in \{1, 2, 3, 5, 8\}} \left( p_{mi}^{\exp(\theta_m)} \right)^{y_i} \left( 1 - p_{mi}^{\exp(\theta_m)} \right)^{n_i - y_i},$$

$y_i$  = the number of DLTs, and  $n_i$  = the number of treated patients in combination  $i$ . The ordering  $h$  with the largest likelihood is chosen and, within this ordering, DLT probability estimates are updated for each combination. If there is a tie between the likelihood values of two or more orderings, then the selected ordering  $h$  is randomly chosen from among the tied orderings. After accrual of each patient cohort into the trial, the DLT probability estimates,  $\tilde{R}(d_i)$ , are updated via

$$\tilde{R}(d_i) = p_{hi}^{\exp(\tilde{\theta}_h)}; \quad \tilde{\theta}_h = \arg \max L_h(\theta_h).$$

The DLT probability estimates are used to sequentially allocate participants according to the following rules:

1. If the most recent participant accrued to the study **does not** experience a DLT, then the recommended combination for the next participant will be the combination indicated by the model to have an estimated DLT rate closest to 25%. Escalation of both agents simultaneously or escalation of more than one dose level of either agent is not allowed.
2. If the most recent participant accrued to the study **does** experience a DLT:
  - a. If the DLT is mucositis or thrombocytopenia or mucositis plus neutropenia and/or thrombocytopenia, then the recommended combination for the next participant will be restricted to either the current combination administered to the most recent participant or to de-escalation of one dose level of Pralatrexate, based on which combination has an estimated DLT rate closest to 25%.
  - b. If the DLT is neutropenia or neutropenia and thrombocytopenia, then the recommended combination for the next participant will be restricted to either the current combination administered to the most recent participant or to de-escalation of one dose level of Decitabine, based on which combination has an estimated DLT rate closest to 25%

The study will sequentially repeat the estimation procedure after the enrollment and follow-up of each cohort. The allocation procedure will be repeated until sufficient information about the MTD has been obtained according to the stopping rules described below.

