### 10.4 Sample size and accrual

A maximum target accrual of 5 additional eligible participants is planned in Arm A (total accrual n=10) and 6 additional eligible participants in Arm C (total accrual n=10). A maximum target accrual of 26 additional eligible participants is planned in Arm B (total accrual n=30), but simulation results below indicate that the average estimated

sample size needed to complete accrual to Arm B is between 3.5 (total accrual n=7.5) and 11.3 (total accrual n=15.3) additional participants. Maximum total sample size for all arms is estimated to be approximately 23 additional participants (total accrual n=36). For estimation of ORR at the MTD, a sample size of 7 at the MTD produces a two-sided 80% binomial confidence interval with a width equal to 0.556 when the sample proportion is 0.5. Additional subjects will be enrolled to replace any subjects who are enrolled, but do not receive treatment. Accrual is estimated at 2 participants per month. Adjusting for an approximate 5% drop-out/ineligibility rate, maximum target accrual should not exceed 38 participants.

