### Arm B

Simulations were run to display the performance of the design characteristics in Arm B using the R statistical programming language. For each scenario, 5000 simulated trials were run using a random seed of 322348. The confidence level used to define the safety stopping guidelines was 80%. Simulation results include the true DLT probability at each combination, the percentage of trials in which each combination was recommended as the MTD, the average number of participants treated at each combination, the average sample size, and the percentage of trials stopped early for safety. The results displayed in the following tables were based upon a maximum target accrual of 30 participants where accrual was stopped when 7 participants were treated on the recommended combination.

Operating characteristics summary for proposed design over five scenarios					
	Scenario 1	Scenario 2	Scenario 3	Scenario 4	Scenario 5
Observed % DLTs	20.25%	21.38%	17.38%	27.27%	31.59%
Average sample size	8.42	8.84	7.51	12.44	15.32
MTD selection % ±5% of target*	92.50%	90.38%	98.70%	22.34%	37.28%
Avg # of pts treated ±5% of target*	6.93	6.91	6.99	2.8	4.4
% of early stopping for safety	0.00%	0.02%	0.00%	0.52%	1.84%

\* Includes combination with highest DLT rate if true DLT probability for all combinations is below 5% of the target

Operating Characteristics						
	True DLT probabilities		MTD Selection Percentage		Average Number of Patients Treated	
Scenario 1						
20mg/m  1,8,15	0.15	0.20	1.36	92.50	0.25	6.93
20mg/m  1,15	0.09	0.14	0.22	5.60	0.08	1.00
15mg/m  1,15	0.07	0.07	0.06	0.26	0.02	0.15
Scenario 2						
20mg/m  1,8,15	0.14	0.25	1.94	90.38	0.33	6.91
20mg/m  1,15	0.10	0.14	0.26	6.64	0.10	1.28
15mg/m  1,15	0.09	0.10	0.04	0.72	0.03	0.20
Scenario 3						
20mg/m  1,8,15	0.08	0.10	0.30	98.70	0.09	6.99
20mg/m  1,15	0.06	0.07	0.00	0.98	0.01	0.39
15mg/m  1,15	0.05	0.05	0.00	0.02	0.00	0.03
Scenario 4						
20mg/m  1,8,15	0.40	0.47	5.00	57.16	0.87	6.52
20mg/m  1,15	0.18	0.25	6.38	22.34	0.89	2.77
15mg/m  1,15	0.15	0.18	1.62	6.98	0.32	1.07
Scenario 5						
20mg/m  1,8,15	0.47	0.55	6.12	34.72	1.25	6.09
20mg/m  1,15	0.25	0.47	18.38	13.10	2.09	2.53
15mg/m  1,15	0.15	0.25	6.94	18.90	1.06	2.31

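### Arm B rule 1 in 10.2 omits a limit on moves after a non-DLT that the 10.5 table, and the 10.4 averages taken from it, appear to assume

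*Protocol*

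**What the plan says.** For a latest participant free of DLT, Protocol 10.2, Arm B, rule 1 reads "then the recommended combination for the next participant will be the combination indicated by the model to have an estimated DLT rate closest to 25" (in percent). The one restriction attached is "Escalation of both agents simultaneously or escalation of more than one dose level of either agent is not allowed". Nothing is said about lowering an agent, or about lowering one while raising the other.

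Rule 2 covers a DLT. Under 2a the choice is between staying and one pralatrexate level down. Under 2b the next assignment "will be restricted to either the current combination administered to the most recent participant or to de-escalation of one dose level of Decitabine". Neither part says what happens when the named agent is already at its lowest level, and some DLT types in 5.3 (grade 4 anemia, for example) fall under neither.

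For Arms A and C, 10.2 does carry a limit after a non-DLT: "next patient will not be treated at a dose level lower than the current dose level if the current patient does not experience a DLT". No such sentence appears for Arm B.

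10.1 gives the starting state: "Based on the accumulated data from the first 4 subjects (1 observed DLT) accrued to Combination 8 in Arm B". 10.5 reports 5,000 simulated trials per scenario, "where accrual was stopped when 7 participants were treated on the recommended combination". 10.4 takes its planning figures from there: "sample size needed to complete accrual to Arm B is between 3.5 (total accrual n=7.5) and 11.3 (total accrual n=15.3) additional participants". Summed over the three arms, it arrives at about 23 further participants, or 36 in all.

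**The concern.** A model-based dose-finding arm is judged on its simulated operating characteristics, so the rule simulated has to be the rule written. If the table in 10.5 came from a more restricted rule than 10.2 states, two things follow. The expected size and selection accuracy quoted for Arm B's primary objective belong to a design that is not the one described. And a statistician applying 10.2 literally can send the next participant to a different combination from the one the simulated design would choose. The second matters more, because it affects assignments and not only planning averages.

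**Working it through.** **Inputs, all from the Protocol.** Five orderings and their skeletons, one-parameter power model, maximum likelihood per ordering, ties broken at random (10.2); target 25% and start at 1 DLT in 4 on Combination 8 (10.1); stop when the recommended combination already has 7, cap of 30, safety bounds at Combination 1 (10.3); true DLT probabilities and printed results (10.5).

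**Assumptions where 10.2 is silent.** The likelihood covers all six combinations. Every DLT is of a type named in rule 2. If the model's choice is barred, the best permitted combination is taken. The share of pralatrexate-type DLTs is not reported, so it was varied from 0 to 1. Runs used 2,000 to 10,000 trials per setting; in the larger runs (6,000 to 10,000) the standard error of a mean size is at most about 0.1.

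**Reproducing the printed table.** Add three things that 10.2 does not state for Arm B: neither agent lowered after a non-DLT, 75% pralatrexate-type DLTs, and the other agent lowered when the named one is at its lowest level. With 10,000 trials:

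| Quantity | Printed | With the three additions |
|---|---|---|
| Mean size, Scenarios 1 to 5 | 8.42, 8.84, 7.51, 12.44, 15.32 | 8.40, 8.83, 7.46, 12.41, 15.37 |
| Scenario 4, mean n at Combinations 1, 2, 3, 5, 6, 8 | 0.32, 1.07, 0.89, 2.77, 0.87, 6.52 | 0.31, 1.08, 0.88, 2.77, 0.86, 6.52 |
| Scenario 4, Combination 8 selected | 57.16% | 57.2% |

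Selection percentages agree to within about 1.1 points throughout.

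**Rule 1 as written**, over all shares from 0 to 1:

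| Quantity | Printed | Rule 1 as written |
|---|---|---|
| Scenario 4 mean size | 12.44 | about 14.1 to 14.7 |
| Scenario 4 mean n at Combination 6 | 0.87 | 2.0 to 2.6 |
| Scenario 4, Combination 8 selected | 57.16% | about 46 to 49% |
| Scenario 5 mean size | 15.32 | about 16.9 to 17.2 |
| Scenario 1 mean n at Combination 6 | 0.25 | about 0.7 to 0.8 |

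No share closes the gap. Staying put when the model's choice is barred leaves it open too (Scenario 4 mean size 14.1 to 14.4, Combination 6 at 1.9 to 2.4). So does adding only the fallback to the other agent (mean sizes 14.1 to 14.7 and 16.6 to 17.2 in Scenarios 4 and 5). What separates the two designs is the up-and-down move after a non-DLT, which occurs at least once in roughly 70% of Scenario 4 trials.

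**A concrete assignment.** Suppose the next participant at Combination 8 has a mucositis DLT, making 2/5. The fitted exponent is ln 0.4 / ln 0.25 = 0.661, so Combination 8 is estimated at 0.40. Combination 5, one pralatrexate level down, is estimated at 0.11^0.661 = 0.23 or 0.174^0.661 = 0.32, depending on the ordering drawn. Either is closer to 0.25 than 0.40, so rule 2a moves to Combination 5.

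Suppose that participant has no DLT. The log-likelihood for each ordering is 2 ln p8 + 3 ln(1 − p8) + ln(1 − p5). Skeleton rows 1 and 5 tie for the highest value (about −3.60 against −3.70 for the rest), with exponent about 0.75. The estimates are then about 0.19 (Combination 5), 0.27 (Combination 6) and 0.35 (Combination 8), at distances from 0.25 of about 0.06, 0.02 and 0.10. Rule 1 as written therefore assigns Combination 6: pralatrexate up one level, decitabine down one. If neither agent may be lowered, or if such swaps are barred, the arm stays at Combination 5.

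**Carrying it into 10.4.** Printed additional participants: 7.51 − 4 = 3.5 to 15.32 − 4 = 11.3. Printed total: 10 + 10 + 15.3 = 35.3, rounded up to 36; 36 × 1.05 = 37.8, rounded up to 38. Under rule 1 as written, Scenario 3 averages from about 7.7 and Scenario 5 up to 17.2, giving 7.7 − 4 = 3.7 to 17.2 − 4 = 13.2 additional. The total is 10 + 10 + 17.2 = 37.2, rounded up to 38; 38 × 1.05 = 39.9, rounded up to 40. At 16.9 the figures are 37 and 39.

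**The case against.** The strongest reply is that the table is sound and only the text is incomplete. A setting close to the Arms A and C limit reproduces all five scenarios, so no printed figure is shown to be miscalculated. That stands. A reader might infer that the 10.5 table is irreproducible or wrong; the documents do not support that.

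The second reply is that the consequences are small. In Scenarios 1 to 3, Combination 8 is still selected in about 90 to 92%, 88 to 89% and 98 to 99% of trials under the literal rule (printed 92.50, 90.38, 98.70). Mean size moves by 0.2 to 0.9 there and by about 2 in Scenarios 4 and 5, against a cap of 30. The direction is mixed: correct selection in Scenario 4 falls to about 16 to 21% (printed 22.34), while selection within 5 points of target in Scenario 5 rises to about 40 to 50% (printed 37.28). 10.4 also labels its total as approximate. This stands as well, and it is why the case rests mainly on the ambiguous next assignment.

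A reader might instead blame the likelihood product in 10.2, whose index set {1, 2, 3, 5, 8} leaves out Combination 6. That is a misprint: 10.1 lists six combinations and every ordering gives Combination 6 a skeleton value. Taken literally it makes the fit far worse, with Combination 6 selected in about 69% of Scenario 4 trials at a 75% pralatrexate-type share (printed 5.00). It does not explain the table and should not be used to widen the range of totals.

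**Conclusion.** The point holds as an inconsistency between 10.2 on one side and 10.5 and 10.4 on the other. Rule 1 as written does not yield the printed Arm B results under any split between the two DLT types that rule 2 names. Scenario 4 mean size is about 2 participants too low in print, and Combination 6 receives less than half the participants that the written rule sends there. The likeliest explanation is a limit on moves after a non-DLT that was simulated but not written for Arm B.

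The fit does not identify that limit. Barring only swaps, with the same fallback and an 80% pralatrexate-type share, also comes close (Scenario 4 mean size 12.6 to 12.7). The DLT-type split and the lowest-level action are likewise inferred from the fit, not documented. A reader might conclude that the Arms A and C limit is the intended Arm B rule; the documents do not establish that.

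Planned size is affected only modestly: about 3.7 to 13.2 additional Arm B participants instead of 3.5 to 11.3, and a total of about 38 (40 with the 5% allowance) against 36 (38). The stopping rules and the cap of 30 are untouched. It should be fixed because the text and the apparently simulated design can assign the next participant differently.

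**What to change.** Check the existing simulation code first, then reconcile 10.2, 10.4 and 10.5 in one of two ways.

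- If the code contains a limit on moves after a non-DLT, write it into 10.2 for Arm B. State also the action when the named agent is at its lowest level, the action when the model's choice is barred, and the action for DLT types that rule 2 does not name, all as simulated. Report in 10.5 the DLT-type split used.
- If rule 1 is meant as written, re-run the Arm B table under it, report the split and the handling of the open cases, and restate the averages and totals in 10.4.

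In either case correct the likelihood index set to include Combination 6. Which allocation rule applies is for the sponsor to decide.

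The cost is a code check plus a text correction, or a short re-run. No additional data are needed. Under a re-run some printed figures become less favourable and others more.

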### 10.3 Stopping rules and MTD definition

#### Arms A and C

Accrual to Arms A and C will be halted and trigger a review by the study investigators and the DSMC to determine if the study should be modified, or permanently closed to further accrual according to the following:

1. Stop the study for safety if the observed DLT rate at the lowest study dose level (Level -2)  $\geq$  the following number of DLTs out of the following number of patients treated at the lowest study dose level. These stopping guidelines are based on whether the lower limit of an Agresti-Coull binomial confidence interval (with 80% confidence) for the lowest study dose level exceeds the target DLT rate. The following bounds were generated using the web application at <http://uvatrapps.uvadcos.io/crmb/>. Note that, given the accrual of previous participants to dose level 1 in Arms A and C, at most 4 participants can be accrued to Level -2 before the maximum sample size is reached.

Stopping guidelines for DLTs at the lowest dose level	
Number of participants	Boundary
2-3	$\geq 2$
4	$\geq 3$

2. If the recommendation is to assign the next patient to a dose level that already has 7 participants treated at the dose level, enrollment to the arm is stopped and the recommended dose level is declared the MTD.
3. Otherwise, the MTD is defined as the dose level that is recommended after the maximum sample size of 10 participants for the arm.

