## **10.0 STATISTICAL CONSIDERATIONS**

### **10.1 Study Design**

This is a Phase Ib study evaluating the safety and efficacy of pembrolizumab combined with pralatrexate (Arm A) or decitabine (Arm C) or decitabine and pralatrexate (Arm B) in patients with peripheral T-cell lymphoma (PTCL) and cutaneous T-cell lymphoma (CTCL). In all arms, toxicity will be assessed according to the NCI Common Toxicity Criteria for Adverse Events (CTCAE), version 5.0. Dose-limiting toxicity (DLT) is a binary outcome (yes/no) and will be determined by adverse events occurring during the first cycle of treatment (see Section 5.3 for DLT definition). In all arms, the maximum tolerated dose (MTD) is defined as the dose combination with a DLT rate closest to the target DLT rate of 25%. The study will accrue participants in cohorts of size 1 in all arms. After accrual of a participant to an arm, the accumulating DLT data will be used to update the model-based estimated DLT

probabilities for each dose level. These estimates will then be used to update the recommended dose level for the next participant accrued to that arm of the study.

Arms A and C:

The primary objectives of Arms A and C is to determine the MTD, defined by acceptable toxicity, of decitabine (Arm C) or pralatrexate (Arm A) (plus a fixed dose of pembrolizumab) from among the 3 study dose levels in the following tables, and to evaluate efficacy, as determined by overall response rate, at the estimated MTD.

Arm A		
Dose Level	Pralatrexate	Pembrolizumab*
Level 1 (start)	30 mg/m  day 1, 8, 15	200 mg day 1
Level -1	30 mg/m  day 1, 15	200 mg day 1
Level -2	20 mg/m  day 1, 15	200 mg day 1

Arm C		
Dose Level	Decitabine	Pembrolizumab*
Level 1 (start)	20 mg/m  day 1->5	200 mg day 8
Level -1	20 mg/m  day 1->3	200 mg day 8
Level -2	10 mg/m  day 1->3	200 mg day 8

Based on the accumulated data from the previous 5 subjects (1 observed DLT) accrued to Arm A, the first eligible subject in Arm A will be entered onto Level 1. Based upon the accumulated data from the previous 4 subjects (2 observed DLTs) accrued to Arm C, the first eligible subject in Arm C will be entered onto Level -1.

Arm B:

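### The lowest-level safety bounds for Arms A and C end at 4 participants, but Arm C can put 5 on Level -2, so 3 DLTs in 5 meets no bound and Level -2 is still declared the MTD

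*Protocol*

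**What the plan says.** Section 10.3 (Arms A and C) halts accrual and calls for review by the investigators and the DSMC when DLTs at the lowest level, Level -2, reach a bound. The bound is met when the lower limit of an 80% Agresti-Coull interval exceeds the 25% target. The table gives 2 DLTs for 2-3 participants and 3 DLTs for 4, and ends there. The reason given is that "at most 4 participants can be accrued to Level -2 before the maximum sample size is reached", in view of those whom both arms have already treated on Level 1. If no bound is met and no level is recommended with 7 already treated on it, the MTD is the level recommended after 10 participants.

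The starting positions are in Sections 10.1 and 10.4:

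- Arm C has treated 4 participants and seen 2 DLTs, and for that reason "the first eligible subject in Arm C will be entered onto Level -1". Section 10.4 then plans "6 additional eligible participants in Arm C (total accrual n=10").
- Arm A has seen 1 DLT in 5, and Section 10.1 says that "the first eligible subject in Arm A will be entered onto Level 1". Section 10.4 gives what remains for this arm: "A maximum target accrual of 5 additional eligible participants is planned in Arm A (total accrual n=10").

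The Arm B table in Section 10.3 uses the same criterion and gives a bound of 3 DLTs for 4-6 participants.

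**The concern.** With 6 participants left in Arm C and the first of them on Level -1, five are left who could go to Level -2. Nothing in Section 10.2 obviously prevents all five from going there, so a ceiling of 4 looks one too low.

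The lowest-level bound is the only numeric safety stop in the arm. If a fifth participant can be treated there, the table has no entry for that count. A DLT rate that the section's own criterion classes as above target would then pass without the formal trigger, and the end-of-accrual rule would name that level the MTD. Determining the MTD is a primary objective.

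**Working it through.** **Inputs.** Target 25% (Section 10.1). Working model: DLT rate at level i equals skeleton value i raised to the power exp(a), with skeleton 0.08, 0.15, 0.25 for Levels -2, -1, 1, and a fitted by maximum likelihood. Cohorts of 1, no skipping, no escalation after a DLT, no de-escalation after a non-DLT (Section 10.2). Printed bounds, the stop at 7 on a level, and 10 participants per arm (Section 10.3).

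**1. The printed bounds reproduce.** With z = 1.2816 (two-sided 80%), let n~ = n + z² and p~ = (y + z²/2)/n~. The lower limit is p~ − z·√(p~(1 − p~)/n~).

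| DLTs / n | Lower limit | Above 0.25? |
|---|---|---|
| 1/2 | 0.164 | no |
| 2/2 | 0.494 | yes |
| 1/3 | 0.102 | no |
| 2/3 | 0.317 | yes |
| 2/4 | 0.230 | no |
| 3/4 | 0.425 | yes |
| 2/5 | 0.179 | no |
| **3/5** | **0.329** | **yes** |
| 3/6 | 0.268 | yes |
| 3/7 | 0.226 | no |
| 4/7 | 0.341 | yes |

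This matches the Arms A and C table for 2-4 participants and the Arm B table up to 7. For 3/5: n~ = 6.642, p~ = 0.575, lower limit 0.329. The bound at 5 participants is therefore 3 DLTs.

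**2. The Arm C start in Section 10.1 agrees with the model.** For 2/4 at Level 1 the fitted rate there is 0.5, so exp(a) = ln 0.5 / ln 0.25 = 0.5. Levels -2 and -1 are then √0.08 = 0.283 and √0.15 = 0.387. Level -2 is closest to 25%, and the no-skipping rule makes the next assignment Level -1, as Section 10.1 states.

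**3. How many can reach Level -2 in Arm C.** Suppose participant 5, on Level -1, has a DLT:

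| Data at Level -2 | Fitted rates, Levels -2 / -1 / 1 | Next level |
|---|---|---|
| none yet | 0.428 / 0.528 / 0.627 | -2 |
| 0/1 | 0.336 / 0.441 / 0.550 | -2 |
| 0/2 | 0.278 / 0.383 / 0.495 | -2 |
| 0/3 | 0.238 / 0.340 / 0.454 | -2 |
| 0/4 | 0.208 / 0.307 / 0.422 | -2 |

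After 0/4 the distances from 0.25 are 0.042 and 0.057, so Level -2 is still closest. Any DLT at Level -2 raises the fitted rates and also keeps the recommendation there. Participants 6 to 10 can all be on Level -2: a maximum of **5**.

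Enumerating every DLT sequence under the full rules confirms this. The maximum is 5 in Arm C from the Section 10.1 start and 3 in Arm A. A maximum of 4 does result for Arm C if 1 DLT in 4 is assumed and the next participant starts on Level 1. One DLT in 4 is the history printed above the Arm C simulation table in Section 10.5.

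**4. Paths that escape the table.** After a DLT at Level -1, the Level -2 sequences (1 = DLT) 0,0,1,1,1; 0,1,0,1,1; and 1,0,0,1,1 each have one DLT at 3 participants and two at 4, so no printed bound is met. They end at 3/5. The fitted rates at 10 participants are 0.528 / 0.619 / 0.704, and Level -2 is named the MTD.

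**5. How often.** Let q be the true rate at Level -1 and p that at Level -2.

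- Five reach Level -2 when participant 5 has a DLT and at most one of the first three on Level -2 does: q × [(1 − p)³ + 3p(1 − p)²].
- Unflagged 3/5: q × 3p³(1 − p)².

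| True rates, Levels -2 / -1 / 1 | Five at Level -2 | Unflagged 3/5 |
|---|---|---|
| 0.05 / 0.15 / 0.25 (Scenario 1) | 15% | 0.005% |
| 0.15 / 0.25 / 0.40 (Scenario 2) | 23% | 0.18% |
| 0.25 / 0.40 / 0.55 (Scenario 3) | 34% | 1.05% |
| 0.40 / 0.55 / 0.65 (assumed) | 36% | 3.8% |

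For Scenario 3: 0.40 × 3 × 0.25³ × 0.75² = 0.0105.

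**The case against.** The arithmetic is not in dispute. The case is that little depends on it.

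- **Nothing is left to halt.** The fifth participant on Level -2 is the tenth in the arm (4 + 1 + 5). Every count at which a halt could still protect an Arm C participant has a printed bound. This stands, and it confines the consequence to the formal review and the MTD declaration.
- **Oversight exists anyway.** Section 10.6 calls the bounds non-binding. Section 9.3.3 has the DSMC meet monthly and review all adverse events and the application of stopping rules. The criterion is also stated in words in Section 10.3, so 3/5 could be judged without a row. This stands in part: the DLTs would be seen, but the table does not flag them and the text tells the reader that the case cannot arise.
- **The frequencies are small and partly benign.** In no Section 10.5 scenario is the true Level -2 rate above target. In Scenario 3 Level -2 is the true MTD, so a flag there would be a false alarm. The 3.8% uses rates that the protocol does not contain, and under them the printed bounds already stop 33% of trials. This stands as a limit on size.
- **It may be a symptom.** The figure 4 fits the Section 10.5 history of 1 DLT in 4, not the 2 in 4 of Section 10.1. That is a plausible origin, but it does not make the sentence right for the start that Section 10.1 prescribes.
- **Requiring review before the MTD is declared is a new rule.** Only weakly: Section 10.3 already triggers review when a bound is met, and its end-of-accrual MTD rule applies only if the earlier rules have not.

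**Conclusion.** The concern holds. The ceiling of 4 is wrong for Arm C as Section 10.1 starts it: the maximum is 5 there and 3 in Arm A. By the plan's own criterion the missing entry is 3 DLTs in 5. Without it, an observed 60% DLT rate at the lowest level meets no bound and that level is declared the MTD.

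The outcome is rare: about 1% or less in the protocol's scenarios, and 3.8% under assumed rates of 0.40 / 0.55 / 0.65. Reaching the uncovered count of 5 is not rare, at 15% to 34% across those scenarios. What is affected is the formal review trigger and the MTD declaration, not further dosing within Arm C.

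The result rests on the Section 10.1 history (2 DLTs in 4, next participant on Level -1) and on the Section 10.2 rules applied exactly as written.

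**What to change.** In Section 10.3, Arms A and C:

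1. Change the sentence to say that at most 3 participants in Arm A and 5 in Arm C can be accrued to Level -2.
2. Replace the table's last row with 4-5 participants, bound 3 or more DLTs. This follows from the stated criterion and agrees with the Arm B table.
3. State that a bound reached by the arm's last participant triggers the DSMC review before an MTD is declared.

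Also reconcile the Arm C history between Section 10.1 (2 DLTs in 4) and Section 10.5 (1 in 4), because the maximum in item 1 depends on it.

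The three changes to Section 10.3 cost two sentences and one table row, with no extra participants. If Arm C has already finished accrual, check whether 5 were treated on Level -2 and apply the completed bound before its MTD is reported.
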